9.4.1. General Considerations

PK analyses will be conducted on data from all participants who receive the complete single dose of lebrikizumab and have sufficient evaluable PK data.

Safety analyses will be conducted for all enrolled participants who receive the single dose of lebrikizumab injection, whether or not they complete all protocol requirements.

Additional exploratory analyses of the data will be conducted as deemed appropriate, and study results may be pooled with the results of other studies for population PK analysis purposes to avoid issues with post hoc analyses and incomplete disclosures of analyses.

9.4.2. Pharmacokinetic Analyses

PK parameter estimates for lebrikizumab will be calculated using standard noncompartmental methods of analysis.

The primary parameters for analysis will be AUC from time zero to time t , where t is the last time point with a measurable concentration ($AUC[0-t_{last}]$), $AUC(0-\infty)$, and C_{max} of lebrikizumab. The time of C_{max} (t_{max}) will also be reported. Other noncompartmental parameters, such as slope of terminal elimination phase, half-life ($t_{1/2}$), apparent oral clearance, and apparent volume of distribution during the terminal elimination phase may be reported as appropriate.

The primary PK parameter estimates for lebrikizumab will be compared between the reference PFS-NSD (R) and test AI (T). Log-transformed C_{max} , $AUC(0-t_{last})$, and $AUC(0-\infty)$ estimates will be evaluated in a linear mixed-effects model with fixed effects for weight group, injection-site location, and device group, and a random effect for participant. The treatment differences will be back transformed to present the ratios of geometric means and the corresponding 90% CIs. Comparisons will be made between the 2 devices.

Bioequivalence between the PFS-NSD and the AI will be declared if the 90% CI for $AUC(0-\infty)$, $AUC(0-t_{last})$, and C_{max} are contained within the 0.80 to 1.25 range.

The t_{max} will be analyzed between the 2 device groups using a Wilcoxon signed rank test. A Hodges-Lehmann estimate of the median differences, 90% CIs, and p-values will be calculated for both treatments.

PK parameter estimates will be summarized by weight category (<70 kg, 70 to 80 kg, and >80 kg) as well as injection-site location (abdomen, arm, thigh) for each device group as appropriate. Additional analyses may be conducted if deemed appropriate.

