1.3. Schedule of Activities (SoA)

Study Schedule Protocol J2T-MC-KGBG

Procedure	Screening	Study Day																	Comments
	-28 to -2 days prior to Day 1	-1	1	3	5 ±1d	8 ±1d	11 ±1d	15 ±2d	22 ±2d	29 ±2d	36 ±2d	43 ±2d	50 ±2d	57 ±2d	64 ±2d	71 ±3d	85 ±3d	99 ±3d or ED	
Informed consent	X																		
Medical history and demographics	X																		
Review and confirm inclusion and exclusion criteria	X	X																	
Admission to CRU		X																	
Discharge from CRU			X																Participants may be discharged after completing the scheduled activities on Day 1, or later at the investigator’s discretion.
Outpatient visit	X			X	X	X	X	X	X	X		X		X		X	X	X	
Safety assessment (telephone call)											X		X		X				To check on the presence of any AEs and concomitant medications.
Randomization			X																Participants will be randomly assigned 1:1 to 1 of 2 delivery devices and 1:1:1 to 1 of 3 injection locations per delivery device.

Procedure	Screening	Study Day																99 ±3d or ED	Comments
	-28 to -2 days prior to Day 1	-1	1	3	5 ±1d	8 ±1d	11 ±1d	15 ±2d	22 ±2d	29 ±2d	36 ±2d	43 ±2d	50 ±2d	57 ±2d	64 ±2d	71 ±3d	85 ±3d		
Height, weight, and BMI	X	X																X	Participant weight at Day -1 will be used for weight category stratification at randomization. Weight, but not height, will be measured on Day -1, and Day 99 or ED.
Physical examination	X	X																X	Full physical examination at screening or at Day -1. Symptom-directed examinations at other times, and as deemed necessary by the investigator.
Vital signs (pulse rate and blood pressure) (sitting), and body temperature	X	X	P, 3hr				X				X							X	Predose Day 1 conducted within 2 hours predose. Postdose assessment 3 ± 1 hour. Time points may be added if warranted at the discretion of the investigator.
Clinical laboratory tests	X	X	P	X			X		X									X	Day 1 conducted within 2 hours predose. See Section 10.2 Appendix 2, Clinical Laboratory Tests, for details.
Serology	X																		See Section 10.2 Appendix 2, Clinical Laboratory Tests, for details.

Procedure	Screening	Study Day																Comments	
	-28 to -2 days prior to Day 1	-1	1	3	5 ±1d	8 ±1d	11 ±1d	15 ±2d	22 ±2d	29 ±2d	36 ±2d	43 ±2d	50 ±2d	57 ±2d	64 ±2d	71 ±3d	85 ±3d		99 ±3d or ED
QuantiFERON®-T B Gold test	X																		
Ethanol test and drug screen	X	X																	Tests may be repeated at additional time points at the discretion of the investigator.

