4.2. Scientific Rationale for Study Design

Conducting the study in healthy participants mitigates the potential confounding effects of the disease state and concomitant medications in participants with AD. A population of healthy participants is frequently used in the assessment of the PK of both small and large molecules.

A single dose of lebrizumab and the PK sampling time points have been selected to generate PK profiles sufficient to fulfill the study objectives.

Participants will be randomly assigned to receive injections in the arm, thigh, or abdomen to evaluate the impact injection site has on bioavailability of lebrizumab.

Previous population PK analyses have shown that patients with a lower body weight tended to have a lower clearance and volume of distribution (Zhu et al. 2017). While the effects of body weight on these PK parameters were statistically significant, it was not considered to be clinically relevant. However, to mitigate these potentially confounding effects, approximately equal numbers of participants in each weight category are proposed to avoid a large difference in mean weight between the test and the reference delivery-device groups. A participant population of 72 per weight group is an approximate target with the recommended weight categories selected based on the distribution of weights in prior studies. The number of participants assigned to each delivery device and the number of participants assigned to each site of injection is desired to be balanced.

A parallel-group design is chosen because a crossover design is impractical for lebrizumab, which has a half-life of approximately 25 days. Additionally, a crossover study could confound PK data if participants develop neutralizing ADAs.

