6.3. Measures to Minimize Bias: Randomization and Blinding

This is an open-label study. In order to minimize potential bias, assignment to treatment groups will be determined by a computer-generated random sequence using an IWRS. On Day 1 (referred to as Visit 1 in IWRS), the site will process Visit 1 in the IWRS prior to the start of study intervention administration and the participant will be assigned a unique subject number and randomized in a 1:1 ratio for delivery device (either PFS-NSD or AI) and within each delivery device group in a 1:1:1 ratio for injection site (arm, thigh, or abdomen) resulting in a 1:1:1:1:1:1 ratio between 6 possible assignment options. The randomization will be stratified by weight categories (less than 70.0 kg, 70.0 to 80.0 kg, and more than 80.0 kg).

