9.2. Sample Size Determination

Approximately 240 participants may be enrolled so that approximately 216 participants (108 in the lebrikizumab PFS-NSD [reference] group and 108 in the AI [test] group) complete the study.

A sample size of 108 participants per device group will provide approximately 90% power that the 90% CI of the geometric mean ratio of maximum observed drug concentration (C_{max}) and area under the concentration versus time curve (AUC) between groups will fall within equivalence range of 0.8 to 1.25. This sample size calculation was based on the assumptions that the PK parameters have log-normal distribution, the percent coefficients of variation (%CV) of C_{max} and AUC are less or equal to 30%, the expected ratio of geometric means is between 0.9 and 1.1, and the %CV are the same for participants from each device group. The 30% CV assumption is based on lebrikizumab PK data in several previous studies.

To properly evaluate AUC from time zero to infinity ($AUC[0-\infty]$), lebrikizumab concentrations must be collected through at least Day 71. To ensure that approximately 216 participants (108 in each group) provide evaluable PK data, approximately 240 participants will be enrolled and receive study drug, assuming up to 10% of the participants may not complete through at least Day 71. Participants who do not complete at least through Day 22 (a period sufficient to determine C_{max}) may be replaced. The replacement participants should be in the same weight category as the original participants.

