## **9.2 Demographics and Participant Disposition**

Participant disposition will be listed. The demographic variables age, sex, race, ethnicity, country of enrolment, site ID, body weight, height, body mass index, weight category, and injection location will be summarized by treatment and listed, both by overall, and using subcategories of weight categories and injection site locations. All other demographic variables will be listed only.

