## **11. CHANGES FROM THE PROTOCOL SPECIFIED STATISTICAL ANALYSES**

The statistical analyses of  $t_{\max}$ , seen in Section 9.3.2, has been changed from a Wilcoxon signed-rank to a Wilcoxon rank-sum test as the study has a parallel design and no correlation is expected between the test and reference groups.

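### Optional precision gain, not an error: the primary model uses body weight only as three groups, and adding log Day -1 weight could modestly narrow the 90% CIs

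*Protocol*

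**What the plan says.** Protocol Section 9.4.2 specifies a model for the three log-transformed primary parameters with "fixed effects for weight group, injection-site location, and device group", plus a participant random effect. Bioequivalence requires the 90% CIs of all three to lie within 0.80 to 1.25.

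The weight groups are the randomization strata of Protocol Section 6.3: "The randomization will be stratified by weight categories (less than 70.0 kg, 70.0 to 80.0 kg, and more than 80.0 kg". The schedule of activities (Section 1.3) shows where the underlying measurement comes from: "Participant weight at Day -1 will be used for weight category stratification at randomization". SAP Section 9.2 already reports both forms: "body weight, height, body mass index, weight category, and injection location will be summarized by treatment and listed".

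On the role of weight, Protocol Section 4.2 says that lower weight went with lower clearance and volume of distribution in earlier population PK work, and adds: "While the effects of body weight on these PK parameters were statistically significant, it was not considered to be clinically relevant". It stratifies so that mean weight does not differ much between devices.

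The SAP's text on the primary PK model is largely blacked out. SAP Section 11 names one departure from the protocol: the t_max analysis "has been changed from a Wilcoxon signed-rank to a Wilcoxon rank-sum test". This point therefore concerns the protocol's model.

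**The concern.** The dose is a fixed 250 mg, so exposure may fall as weight rises. Two of the three weight groups have no outer bound in kilograms, and any trend of exposure with weight inside a group stays in the residual. A pre-dose measurement that could explain part of that residual is already collected but not used in the readable model.

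Only precision is at stake. The model contains the stratification factor, and a chance weight imbalance within groups is sampling error that the planned interval already covers. Precision still has some value: all three intervals must pass, so the probability of declaring bioequivalence cannot exceed the power for any single parameter. At a true ratio of 0.9, 108 per device is the smallest number that gives 90%.

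**Working it through.** **Inputs from the documents** (Protocol Section 9.2): 108 per device, limits 0.80 to 1.25, 90% CI, CV at most 30%, expected ratio 0.9 to 1.1.

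**The plan's own figure.** The log-scale variance is ln(1 + 0.30²) = 0.0862, so the SD is 0.2936. Each participant contributes one value per parameter, so the participant random effect cannot be separated from the residual. The fit is ordinary least squares with 216 − 6 = 210 degrees of freedom. The standard error is 0.2936 × √(2/108) = 0.0399, and the 90% half-width is 1.652 × 0.0399 = 0.0660. Exact power of the two one-sided tests is 90.2% at ratio 0.9, 99.6% at 0.95 and 93.9% at 1.1. The stated power of about 90% reproduces.

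**Assumptions, none of them in the documents**
- Log exposure is linear in log weight, with absolute slope b between 0.25 and 1.0.
- Weight is log-normal with median 76 kg and log-SD 0.13 to 0.19, limited to 45–120 kg.
- One third of participants fall in each weight group.
- 30% is the CV that remains after the weight-group term.

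**Weight variation left inside the groups.** The within-group log-SDs are 0.065, 0.038 and 0.069 (population SD 0.13), or 0.094, 0.038 and 0.094 (SD 0.19). The mean within-group variance V is 0.00346 or 0.00643. The three groups already capture 81% or 79% of the variance of log weight.

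**Gain and cost.** The covariate removes a fraction r = b²V / 0.0862 of the residual variance. The smallest case is 0.0625 × 0.00346 / 0.0862 = 0.25%. The largest is 0.00643 / 0.0862 = 7.5%. On their own these narrow the interval by 1 − √(1 − r), which is 0.1% to 3.8%. The covariate costs one degree of freedom (210 to 209) and inflates the variance of the device contrast by about 1 + 1/209. The net width ratio is approximately √[(1 − r)(1 + 1/209)].

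| Absolute slope | Mean CI width vs planned (SD 0.13 / 0.19) | Power at ratio 0.9 | Trials with a wider CI |
|---|---|---|---|
| 0 | 1.0024 | 90.1% | – |
| 0.25 | 1.0012 / 1.0001 | 90.2% | 61–70% |
| 0.5 | 0.9975 / 0.9930 | 90.4–90.6% | 27–46% |
| 1.0 | 0.9820 / 0.9648 | 91.1–92.0% | 1–8% |

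The widths and the last column come from 20,000 simulated trials per setting (12 per cell, 18 cells, fitted with and without log weight). The formula agrees: at b = 1.0 and SD 0.19, √(0.9254 × 1.0048) = 0.964.

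**Break-even.** The width is unchanged when r = 1 − 1/(1 + 1/209) = 0.0048, that is b = √(0.0048 × 0.0862 / V). This gives about 0.34 for V = 0.00346 and 0.25 for V = 0.00643.

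**The case against.** The strongest reply is that this is a refinement of a sound model. The stratification factor already takes up about four fifths of the weight variance, the stated power is met, and the 30% CV is a ceiling (Protocol Section 9.2: "AUC are less or equal to 30" percent). The documents give the direction of the weight effect but no slope, and they give it for patients. Below a slope of about 0.25 to 0.35 the covariate does not help on average.

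The effect on the result is also small. At an observed ratio of 1.0 the planned lower limit is exp(−0.0660) = 0.9361. A slope of 0.5 moves it to between 0.9363 and 0.9366, and the best case moves it to 0.9383. The top of the range may be generous. A slope of 1.0 means a 100/60 = 1.67-fold exposure difference between 60 and 100 kg, which fits poorly with a weight effect judged not clinically relevant. The BMI limit of 32 in Protocol Section 5.1 also makes very heavy participants rare. Under an illustrative 50–105 kg range, the best case falls from about 3.5% to about 2.4% narrower. A single slope for Cmax and both AUCs is a simplification too.

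All of this stands as a limit on the size of the gain. It does not remove the point: clinical irrelevance does not settle whether weight explains residual variance, and the average loss is at most 0.24% in width. The blacked-out SAP text might contain a weight-based sensitivity analysis, so its absence cannot be asserted.

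**Conclusion.** The point holds as an optional improvement. Nothing in the planned analysis is wrong and the sample size is adequate on its own assumptions. Under the assumptions above, adding log weight changes the average 90% CI width by between +0.1% and −3.5%, and raises power at ratio 0.9 by 0 to 1.8 percentage points. The worst case is an average widening of 0.24% when weight has no effect within groups. Confidence in the size is moderate, because the slope and the weight distribution are assumed and the SAP's model text cannot be read. The sponsor's earlier lebrikizumab PK data should be able to settle the slope.

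**What to change.** Before the SAP is signed, pre-specify log(Day -1 body weight) as an additional continuous covariate in the primary model for Cmax, AUC(0-tlast) and AUC(0-∞). Keep weight group, injection-site location and device in the model, and record the change in SAP Section 11. The timing matters because the study is open-label: a covariate chosen after data are seen would carry less weight.

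Check the slope in the earlier PK data first. If its absolute value is below about 0.25 to 0.35, keep the planned model as primary and pre-specify the log-weight model as a sensitivity analysis.

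The cost is a few lines of SAP text, one degree of freedom and a log-linear working assumption. No new data are needed.

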9.4.3. Safety Analyses

All safety analyses will be made on the Safety Population. All AEs will be listed, and if the frequency of events allows, safety data will be summarized using descriptive methodology. The incidence of AEs for each device will be presented by severity and by association with lebrikizumab as perceived by the investigator. AEs reported to occur prior to study entry will be distinguished from those reported as new or increased in severity during the study. Each AE will be classified by the most suitable term from Medical Dictionary for Regulatory Activities. The number of SAEs will be reported.

9.4.4. Evaluation of Immunogenicity

The frequency and percentage of participants with preexisting ADAs and with TE-ADAs to lebrikizumab will be tabulated. TE-ADAs are defined as those with a titer 2-fold (1 dilution)

greater than the minimum required dilution if no ADAs were detected at baseline (treatment-induced ADA) or those with a 4-fold (2 dilutions) increase in titer compared to baseline if ADAs were detected at baseline (treatment-boosted ADA). For the TE-ADA subjects, the distribution of maximum titers will be described. The frequency of neutralizing antibodies will also be tabulated in TE-ADA subjects. The relationship between the presence of antibodies and the safety and PK parameters to lebrikizumab may be assessed.

9.5. Interim Analyses

No interim analyses are planned for this study. If an unplanned interim analysis is deemed necessary the Lilly clinical pharmacologist, investigator, or designee will consult with the appropriate medical director or designee to determine if it is necessary to amend the protocol.

9.6. Data Monitoring Committee (DMC)

No data monitoring committee is required for this study.

10. Supporting Documentation and Operational Considerations

10.1. Appendix 1: Regulatory, Ethical, and Study Oversight Considerations

10.1.1. Regulatory and Ethical Considerations

This study will be conducted in accordance with the protocol and with the following:

- Consensus ethical principles derived from international guidelines including the Declaration of Helsinki and Council for International Organizations of Medical Sciences International Ethical Guidelines
- Applicable ICH GCP Guidelines
- Applicable laws and regulations

The protocol, protocol amendments, ICF, Investigator's Brochure, and other relevant documents (for example, advertisements) must be submitted to an IRB/IEC by the investigator and reviewed and approved by the IRB/IEC before the study is initiated.

Any amendments to the protocol will require IRB/IEC approval before implementation of changes made to the study design, except for changes necessary to eliminate an immediate hazard to study participants.

The investigator will be responsible for the following:

- Providing written summaries of the status of the study to the IRB/IEC annually or more frequently in accordance with the requirements, policies, and procedures established by the IRB/IEC
- Notifying the IRB/IEC of SAEs or other significant safety findings as required by IRB/IEC procedures
- Providing oversight of study conduct for participants under their responsibility and adherence to requirements of 21 Code of Federal Regulations, ICH guidelines, the IRB/IEC, European regulation 536/2014 for clinical studies (if applicable), and all other applicable local regulations

Investigator sites are compensated for participation in the study as detailed in the clinical trial agreement.

10.1.2. Informed Consent Process

The investigator or his/her representative will explain the nature of the study, including the risks and benefits, to the participant or his/her legally authorized representative and answer all questions regarding the study.

Participants must be informed that their participation is voluntary. Participants or their legally authorized representative will be required to sign a statement of informed consent that meets the requirements of 21 Code of Federal Regulations 50, local regulations, ICH guidelines, Health Insurance Portability and Accountability Act requirements, where applicable, and the IRB/IEC or study center.

The medical record must include a statement that written informed consent was obtained before the participant was entered in the study and the date the written consent was obtained. The authorized person obtaining the informed consent must also sign the ICF.

Participants must be re-consented to the most current version of the ICF(s) during their participation in the study.

A copy of the ICF(s) must be provided to the participant or the participant's legally authorized representative and is kept on file.

10.1.3. Data Protection

Participants will be assigned a unique identifier by the sponsor. Any participant records, datasets, or tissue samples that are transferred to the sponsor will contain the identifier only; participant names or any information that would make the participant identifiable will not be transferred.

The participant must be informed that his/her personal study-related data will be used by the sponsor in accordance with local data protection law. The level of disclosure must also be explained to the participant who will be required to give consent for his/her data to be used as described in the informed consent.

The participant must be informed that his/her medical records may be examined by Clinical Quality Assurance auditors or other authorized personnel appointed by the sponsor, by appropriate IRB/IEC members, and by inspectors from regulatory authorities.

The sponsor has processes in place to ensure data protection, information security, and data integrity. These processes include appropriate contingency plan(s) for appropriate and timely response in the event of a data security breach.

10.1.4. Dissemination of Clinical Study Data

Communication of suspended or terminated dosing

If a decision is taken to suspend or terminate dosing in the trial due to safety findings, this decision will be communicated by Lilly to all investigators (for example, through phone and/or email) as soon as possible. It will be a requirement that investigators respond upon receipt to confirm that they understand the communication and have taken the appropriate action prior to further dosing any participants with study intervention. Any investigator not responding will be followed up by Lilly personnel prior to any further planned dosing. If a dose is planned imminently, Lilly personnel will immediately, and continually, use all efforts to reach investigators until contact is made and instructions are verified.

Reports

The sponsor will disclose a summary of study information, including tabular study results, on publicly available websites where required by local law or regulation.

Data

The sponsor does not proactively share data from Phase 1 clinical trials. Requests for access to Phase 1 clinical trial data are evaluated on a case-by-case basis taking into consideration the ability to anonymize the data and the nature of the data collected.

